#### Part B:

The Part B trial is an open-label trial.

#### 3.5 Trial Treatment

#### 3.5.1 Investigational Products

#### 3.5.1.1 CP101

CP101 is an investigational oral microbiome drug designed to deliver a complete and functional microbiome to durably repair intestinal dysbiosis, which is being evaluated for the prevention of recurrent CDI.

CP101 contains live microbial communities, derived from rigorously screened human donor stool that is tested, stabilized, characterized, and formulated into capsules

### 3.5.1.2 Placebo

Because this is a double-blind, placebo-controlled trial (Part A), placebo will be presented in capsules that are identical in size, smell, texture, and appearance to those of the CP101 capsules.

#### 3.5.2 Investigational Product Administration

In Part A, IP (either CP101 or matching placebo) will be administered after Randomization on Day 1 (single administration) as an oral dose

In Part B, all participants will be treated with a single dose of CP101 administered orally by capsules

#### 3.5.3 Investigational Product Packaging and Labeling

The IP will be packaged and labeled by the Sponsor in accordance with applicable Good Manufacturing Practice and local regulatory requirements.

The Investigator or designee must confirm appropriate temperature conditions have been maintained during transit for all IP received and any discrepancies are reported and resolved before use of the IP.

Refer to the Pharmacy Manual for additional information.

## 3.5.4 Storage of Investigational Product

All IP bottles are to be stored accordance with the storage requirements outlined in the Pharmacy Manual.

All IP must be stored in a secure, environmentally controlled, and monitored (manual or automated) area in accordance with the labeled storage conditions with access limited to the Investigator and authorized site staff.

Refer to the Pharmacy Manual for additional information.

### 3.6 Trial Duration

Following a 6-week Screening period, the trial duration will be approximately 24 weeks after the IP administration for participants in Part A who do not experience an on-trial, central laboratory-positive *C. difficile*-related diarrhea through Week 8. This includes an 8-week efficacy and safety assessment and an additional safety and CDI recurrence follow-up through Week 24.

Participants who enter Part B of the trial will be followed through Week 24 following OLT. This includes an 8-week efficacy and safety assessment and an additional safety and CDI recurrence follow-up through Week 24.

### 3.7 Discontinuation Criteria

### 3.7.1 Criteria for Trial Termination

The Sponsor may terminate this trial at any time. Reasons for termination may include but are not limited to, the following:

• New information regarding the safety or efficacy of the IP that indicates a change in the known risk/benefit profile for the compound, such that the risk/benefit is no longer acceptable for participants participating in the trial, as assessed by the Sponsor;

- Significant violation of International Council for Harmonization (ICH) Good Clinical Practice (GCP) that compromises the ability to achieve the trial objectives or compromises participant safety;
- Insufficient participant enrollment; and
- Sponsor decision.

# 3.7.2 Participant Withdrawal

A trial participant (or legal guardian acting on behalf of the participant) is free to withdraw consent and discontinue participation in the trial at any time, without prejudice to further treatment according to standard clinical practice. A participant's participation in the trial may be discontinued at any time at the discretion of the Investigator or Sponsor if, for example:

- The participant is noncompliant with the trial responsibilities.
- Participant withdraws consent and refuses to continue procedures/assessments.
- The Sponsor terminates the trial.
- The Investigator determines it is no longer in the participant's best interest to participate in the trial.
- After at least 3 reasonable attempts to make contact, including final contact via certified mail, the participant is lost to follow-up.

Participants who have discontinued IP by receiving a partial dose (as applicable) are encouraged to remain in the trial and to continue to complete trial assessments to the extent possible. If a participant or the participant's legal guardian, acting on behalf of the participant, discontinues participation in the trial, or the participant is discontinued by the Investigator or Sponsor, the Early Termination Case Report Form (CRF) describing the reason for discontinuation must be completed.

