# 1.6.1 Dose for this Clinical Trial

Participants will be randomized in a 2:1 ratio into 1 of 2 treatment groups to receive 1 of the following:

• CP101: Single oral dose of CP101

• **Placebo**: Single oral dose of placebo that are identical in size, smell, texture and appearance to those of the CP101 capsules.

**Duration of Treatment**: The treatment period will be 1 day, and participants will be monitored through Week 24 for long-term safety outcomes following Randomization.

Blinded IP will be administered

under direct supervision of trial staff.

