### 2.1 Primary Efficacy Objective, Endpoint, and Estimand

Primary Objective	Primary Endpoint
To evaluate the efficacy of a single oral dose of CP101 compared to placebo following SOC CDI antibiotics in preventing CDI recurrence in participants with recurrent CDI	Proportion of participants experiencing a CDI recurrence through Week 8 based on adjudication

The primary clinical question of interest is:

What is the difference in the proportions of participants experiencing CDI recurrence through 8 weeks after randomization to CP101 vs placebo in participants with recurrent CDI regardless of discontinuation of investigational intervention for any reason or change in background medication (dose and product)?

The estimand is described by the following attributes:

• Population:

Adult participants with recurrent CDI who have completed SOC CDI antibiotics for their qualifying episode

• Endpoint:

CDI recurrence through 8 weeks post randomization

• Treatment condition:

CP101 or placebo on Day 1 with 8 week follow-up for recurrence regardless of discontinuation of investigational intervention for any reason, or change in background medication (treatment policy strategy).

• Remaining intercurrent events:

The intercurrent events "intervention discontinuation for any reason" and "change in background medication (dose and product)" are addressed by the treatment condition of interest attribute.

The following intercurrent events will result in an outcome of "recurrence" for the primary efficacy analysis:

- Initiation of rescue medication for CDI (fecal microbiota transplantation [FMT] or full course of SOC antibiotics) prior to 8 weeks post randomization
- Occurrence of *C. difficile*-related diarrhea prior to 8 weeks in a participant who does not qualify for Part B of the study, per central lab testing algorithm, and discontinues the study for any reason
- Participants who enter into Part B of the study however, the *C. difficile*-related diarrhea episode is adjudicated as "no recurrence" by the AB
- Participants who die or experience another debilitating event prior to 8 weeks, which precludes continued participation in the study
- Participants who withdraw consent prior to 8 weeks after randomization
- Participants who are lost to follow-up prior to 8 weeks after randomization

There are no other intercurrent events anticipated at this time.

• Population-level summary:

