5.2 Diet

# 5.1.2 Concomitant Therapy and Restricted Medications

# 5.3 Participant Compliance

Investigational product will be administered as a single oral dose under the direct supervision of trial staff on Day 1.

Investigational product accountability must be performed by the trial staff on the day of the visit and recorded on the accountability log, in order to ensure that the participant is compliant with trial requirements. Investigational product accountability is also recorded in the CRF and checked by the Monitor during site visits.

Deviation(s) from the prescribed

dosage regimen should be recorded.

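### Section 3.7.2 lets a participant be removed for noncompliance; after the single Day 1 dose this mainly creates avoidable missing Week 8 data

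*Protocol*

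**What the plan says.** Section 3.7.2 gives a discretionary power to end participation in the trial as a whole: "A participant's participation in the trial may be discontinued at any time at the discretion of the Investigator or Sponsor if, for example". The first ground listed is "The participant is noncompliant with the trial responsibilities". The visible text does not define these responsibilities and sets no threshold. It neither exempts the period before Week 8 nor attaches a safety condition. The same section encourages participants who took only part of the dose to stay in the trial; it says nothing similar about fully dosed participants who miss assessments.

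Dosing is brief. Section 1.6.1 states "The treatment period will be 1 day", and Section 5.3 states "Investigational product will be administered as a single oral dose under the direct supervision of trial staff on Day 1".

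Section 2.1 describes the treatment condition as "CP101 or placebo on Day 1 with 8 week follow-up for recurrence regardless of discontinuation of investigational intervention for any reason". It handles leaving the study separately. Among the events counted as recurrence are "Participants who withdraw consent prior to 8 weeks after randomization" and "Participants who are lost to follow-up prior to 8 weeks after randomization". Removal for noncompliance is not on that list, which closes with "There are no other intercurrent events anticipated at this time".

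Section 8.3 makes all randomized participants the primary efficacy population, and Section 3.7.3 rules out replacement. Section 3.3 names two primary endpoints, both through Week 8: CDI recurrence and the incidence of treatment-emergent adverse events.

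After a withdrawal, Section 3.7.2.1 asks for information where possible and for an early termination visit. In Table 3 that visit includes a recurrence assessment. Section 3.7.4 adds a follow-up no later than 4 weeks after withdrawal for those who received the product but did not complete the trial.

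**The concern.** In a trial with repeated dosing, a noncompliance clause can serve to stop further exposure. Here, once the Day 1 dose has been swallowed under supervision, no Part A treatment is left to stop. Noncompliance after that point can only concern matters such as diaries, samples, visits and contacts. Removal on that ground turns incomplete data into no further data, for a participant who has neither withdrawn consent nor been lost.

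The stake is avoidable missingness in both Week 8 primary endpoints. Recurrence is detected through diary entries and self-report, so poor compliance could plausibly be related to symptoms; the documents do not show that it is. Each removed participant stays in the denominator. Unless a recurrence was already established, the outcome must be assigned by rule when it might have been observed.

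**Working it through.** **1. Related figures the protocol does state.** It gives no removal rate, so nothing on this exact point can be reproduced. Two neighbouring figures do reproduce:
- Interim fraction (Section 8.10): 217/324 = 0.6698, matching the stated 67%.
- Prior controlled trial (Section 1.5.2): 74.5% vs 61.5%, n = 198. The only nearby integer split tried that returns these percentages is 76/102 vs 59/96. An uncorrected chi-square test gives p = 0.0488, as printed.

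I read the printed percentages as recurrence-free rates, which is an assumption. Recurrence is then 25.5% on CP101 and 38.5% on placebo, a difference of 13.0 points.

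**2. Do the existing safeguards reach Week 8?** Week 8 is Day 57 ± 3 (Table 3). Follow-up is due within 28 days of withdrawal.
- 57 − 28 = Day 29. For anyone removed before Day 29, the window closes before Day 57.
- Against the earliest permitted Week 8 day: 54 − 28 = Day 26.

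The early termination visit records recurrence status at exit, not at Week 8. Both safeguards reduce the loss, and neither guarantees a Week 8 outcome.

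**3. How many participants?** With 2:1 allocation, 324 splits into 216 and 108. The removal fraction x is assumed equal in both arms.
- x = 1%: 324 × 0.01 = 3.2, about 3 participants
- x = 5%: 324 × 0.05 = 16.2, about 16 participants

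**4. Effect if all removals are coded alike.** If every removal counts as a recurrence, each arm's rate becomes p(1 − x) + x. The added x cancels between arms, so the difference is 13.0 × (1 − x).
- x = 1%: 13.0 × 0.99 = 12.87 points
- x = 3%: 13.0 × 0.97 = 12.61 points
- x = 5%: 13.0 × 0.95 = 12.35 points

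Illustrative power (normal approximation, 216 vs 108, two-sided 0.05 assumed) is 67.0% with no removals, 65.6% at 1% and 60.2% at 5%. These are not the trial's planned power, whose inputs are not visible.

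**5. Extreme-case bounds.** Suppose every removed participant recurs in one arm and none does in the other. The difference then lies in 13.0 × (1 − x) ± 100x, a width of 200x points.

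| x | Lower | Upper | Width |
|---|---|---|---|
| 1% | 11.87 | 13.87 | 2 |
| 3% | 9.61 | 15.61 | 6 |
| 5% | 7.35 | 17.35 | 10 |

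The table shows what the data could not exclude, not what is expected.

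**The case against.** A reader might infer that the clause contradicts the treatment-policy estimand. The documents do not support that. The Section 2.1 wording concerns discontinuation of the investigational intervention or a change in background medication, and exit from the study is treated separately. The tension is with the aim of 8-week follow-up, not with the text.

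A reader might also set the 10-point width at 5% beside the prior trial's 13-point difference and see a serious threat. That width needs opposite outcomes in the two arms at an assumed rate. Sections 3.4.2 and 8.2 keep the Investigator and Sponsor blinded at least until the Week 8 lock, which makes removal that differs by arm less likely.

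A third tempting reading is that such removals have no scoring rule. Section 2.1 does not list them, but the content of Section 8.9 on missing data is not visible and a statistical analysis plan may exist. Some removals are covered in any case, for example where rescue treatment has already started. A missing rule is not the point here.

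Other objections stand in part:
- The clause permits removal and does not require it. Examples such as missed diaries are inferred, because the protocol text does not define the responsibilities.
- Removal ends more than outcome collection: it also ends possible entry to open-label Part B.
- A participant whose recurrence was established before removal already has an outcome.
- Under Section 7.1.2.1, ascertainment depends on reported diarrhea, a stool sample and adjudication. Someone who will not report or give a sample may have no adjudicable outcome even if retained, so the fix recovers only part of the loss.
- Deleting one item from a list offered only as examples would leave the discretion intact.

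None of these gives a reason to end follow-up for noncompliance alone.

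**Conclusion.** The point holds as a matter of avoidable missing data. After the single supervised dose, the noncompliance ground in Section 3.7.2 mainly allows Week 8 recurrence and adverse-event follow-up to be ended early, and the existing post-withdrawal steps do not secure a Week 8 outcome for participants removed before about Day 29.

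The size is unknown and probably modest. At the assumed 1% to 5%, uniform coding as recurrence costs roughly 0.1 to 0.6 points of a 13.0-point difference (13.0 − 12.87 = 0.13; 13.0 − 12.35 = 0.65). This rests on three assumptions: the removal rate, equal removal in both arms, and the prior trial's percentages being recurrence-free rates. If removals are rare, the effect is negligible. The case for changing the text is that the loss is preventable at almost no cost.

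**What to change.** In Section 3.7.2:
1. Remove noncompliance with trial responsibilities as a ground for ending participation before Week 8.
2. Because the list is only illustrative, add an explicit sentence such as: Dosed participants who miss diary entries, samples or visits remain in recurrence and safety follow-up through Week 8, using the scheduled contacts, unless they withdraw consent or the Investigator judges that continuing is not in their best interest.

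The second change does most of the work. The other listed grounds (consent, best interest, trial termination, loss to follow-up) stay as they are.

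Table 3 already provides telephone or virtual contacts at Weeks 1 and 4 and an on-site or home visit at Week 8, so no new visit is needed. The cost is a short protocol amendment and continued contact with a few participants. The downside is that some with incomplete diaries or samples stay in follow-up, and some of these may still lack an adjudicable outcome.

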# 3.7.2.1 Collection of Data from Withdrawn Participants

Whenever possible, Investigators should attempt to obtain information about participants in the case of withdrawal from the trial. Results of any evaluations and observations, together with a narrative describing the reason(s) for withdrawal from the trial, must be recorded in the source documents. The CRF must document the primary reason for withdrawal from the trial.

If the reason for withdrawal from the trial is an AE and/or clinically significant abnormal laboratory test result, the Investigator will continue to monitor the event until the event has resolved or stabilized, until the participant is referred to the care of a health care professional, or until a determination of a cause unrelated to the IP or trial procedure is made. The specific event or test result (including repeated test results, as applicable) must be recorded both on the source documentation and in the CRF; both the AE page and the relevant page of the CRF will be completed at that time. As soon as possible, the Investigator must inform the Sponsor about each participant who is being considered for withdrawal due to AEs. Additional reports must be provided when requested.

If a participant is withdrawn from the trial for multiple reasons that include AEs, the relevant page of the CRF should indicate the withdrawal was related to an AE.

In the case of participants lost to follow-up, attempts to contact the participant must be made and documented in the participant's medical records.

An early termination visit should be conducted for all participants who were randomized but do not complete the trial according to the trial protocol.

# 3.7.3 Participant Replacement

There is no provision for replacing participants.

# 3.7.4 Participant Follow-Up

Follow-up within 4 weeks from the date of withdrawal will be conducted for all participants who receive the IP but do not complete the trial according to the trial protocol.

# **3.8** Trial Material Accountability

The Investigator will ensure that adequate records showing the receipt, dispensing, return, or other disposition of the IP, including the date, quantity, batch or code number, and identification of trial participants who receive the IP are maintained. The Investigator will not supply the IP to any person except Sub-Investigators (as submitted to the local regulatory authority), designated staff, and participants in this trial. The Investigator will not dispense the IP from any sites other than those submitted to the local regulatory authority. The IP will not be relabeled or reassigned for use by other participants.

Each IP shipment will include a packing slip listing the contents of the shipment, return instructions, and any applicable forms.

The Investigator is responsible for ensuring deliveries of the IP and other trial materials from the Sponsor are correctly received, recorded, handled, and stored safely and properly in accordance with applicable regulatory requirement, and used in accordance with this protocol.

Only participants enrolled in the trial may receive the IP and only authorized staff at the investigational center may supply or administer the IP, which must be stored in a secure, environmentally controlled, and monitored (manual or automated) area in accordance with the labeled storage conditions or appropriate instructions with access limited to the Investigator and authorized staff at the investigational center.

A record of IP accountability (i.e., IP and other trial materials received, used, retained, returned, or destroyed) must be prepared and signed by the principal Investigator or designee with an account given for any discrepancies. Upon completion of the trial, unused IP will be returned to the Sponsor's designee or destroyed locally per the Pharmacy Manual.

# 4 SELECTION AND WITHDRAWAL OF PARTICIPANTS

The trial will include approximately 324 participants from approximately 100 centers.

# Inclusion Criteria Part A (Screening):

- 1. Participant or legal representative voluntarily agreed to participate by signing and dating the written informed consent form after trial has been fully explained.
- 2. Participant 18 years of age or older.
- 3. History of recurrent CDI defined as:
  - 3.1  $\geq$  3 episodes of CDI, with 2 episodes occurring within the previous 6 months (inclusive of the current episode); OR

- 3.2 Participants with a history of 2 episodes of CDI occurring within the previous 6 months (inclusive of the current episode) may be eligible if 65 years of age or older.
- 4. For the qualifying CDI episode, the following criteria (4.1-4.4) must be satisfied:
  - 4.1 History of diarrhea (> 3 unformed stools per day) for 2 or more consecutive days that is clinically consistent with CDI.
  - AND
  - 4.2 Documented positive stool test by local laboratory for toxigenic *C. difficile* (toxin EIA or polymerase chain reaction [PCR]-based testing) for the current CDI episode and within 45 days prior to Randomization.

#### AND

4.3 Received a course of SOC CDI antibiotics for the most recent CDI episode (for 10 to 21 days, with exact duration, antibiotic type, and dose at the discretion of the Investigator);

#### AND

4.4 Demonstrated an adequate clinical response, defined as  $\leq 3$  unformed stools in 24 hours for 2 or more consecutive days during SOC CDI antibiotics prior to Randomization.

# **NOTE**: ALL Qualifying CDI episode requires CLINICAL and LABORATORY CONFIRMATION of eligibility by Medical Monitor.

- 5. Females (assigned at birth) must fulfill at least 1 of the following criteria:
  - 5.1 Postmenopausal, defined as amenorrhea  $\geq 1$  year; or
  - 5.2 Surgically sterile: hysterectomy, bilateral oophorectomy, or tubal ligation; or
  - 5.3 Abstinent or willing to use adequate contraception from Screening through the Week 24 visit per Section 7.2.9.1.
- 6. Males (as assigned at birth) must fulfill the following criteria: Abstinent or willing to use adequate contraception from Screening through the Week 24 visit per Section 7.2.9.1.

# Exclusion Criteria Part A (Screening):

- 1. Known stool samples testing positive for enteric pathogens (e.g., *Salmonella*, *Shigella*, diarrhoeagenic *E. coli*, *Campylobacter*, *Giardia*) within 28 days prior to Screening.
- 2. Inability to ingest capsules (e.g., severe nausea, vomiting, gastroparesis, gastric outlet obstruction, dysphagia and/or history of chronic aspiration).
- 3. Active or suspected ileus, toxic megacolon, or bowel obstruction.
- 4. Historical or current diagnosis of inflammatory bowel disease (e.g., Crohn's disease, ulcerative colitis, indeterminate colitis, or microscopic colitis).
- Recent diagnosis (< 6 months prior to Screening) of diarrhea-predominant irritable bowel syndrome (post-infection or not related to an enteric infection). Participants with diarrhea-predominant irritable bowel syndrome ≥ 6 months prior to Screening may be randomized following confirmation of eligibility.

- 6. Current diagnosis of chronic diarrheal illness with pre-CDI baseline diarrhea. This includes but is not limited to celiac disease, bile salt diarrhea, chronic pancreatitis, and short gut syndrome.
- Past administration of bezlotoxumab (Zinplava™), or past enrollment in a *C. difficile* vaccine trial where participant received active investigational product (IP) within 12 months prior to Randomization. Participants blinded to treatment assignment or with unknown status are excluded. Participants who only received placebo would not be excluded.
- 8. Participation in PRISM3 (CDI-001) or PRISM-EXT (CP101-CDI-E02) where participant received active IP or received CP101 at any time in the past. Participants who only received placebo would not be excluded.
- 9. Fecal transplant or other live microbiome therapeutics for any condition, regardless of route of administration within 12 months prior to Randomization.
- 10. Initiation of any systemic cancer treatment (e.g., chemotherapy, radiotherapy, biologic, immunotherapy, others) for active malignancy that is planned 8 weeks prior to Randomization or during the 8 weeks following Randomization. Participants on maintenance treatment for malignancy may be randomized following confirmation of eligibility. NOTE: Participants on hormone therapy alone are eligible.
- 11. Known primary or secondary immunodeficiency, including but not limited to, IgA deficiency, common variable immunodeficiency, severe combined immunodeficiency, or human immunodeficiency virus/acquired immune deficiency syndrome.
- 12. History of solid organ transplantation or stem cell transplant.
- 13. Initiation or dose escalation of systemic immunosuppressive agents, at the discretion of the Investigator, for any condition during the 8 weeks prior to Randomization or planned during the 8 weeks following Randomization. Examples may include but are not limited to corticosteroid agents given orally or intravenously, cyclosporine, tacrolimus, or tumor necrosis factor inhibitors. Participants on stable low dose of systemic immunosuppressive agents or short courses (< 2 weeks) may be randomized following confirmation of eligibility.
- 14. Major intra-abdominal surgery (e.g., bowel resection) within the past 60 days prior to Screening (excluding appendectomy or cholecystectomy) and/or planned invasive surgery/hospitalization during the trial.
- 15. History of total colectomy or ileostomy.
- 16. Use of a systemic antibiotic for any condition (other than CDI) during the Screening period, or any anticipated use of a systemic antibiotic for any condition other than CDI during the trial for 8 weeks after Randomization. This includes participants who have a known medical procedure that requires antibiotic prophylaxis (e.g., elective surgical procedure or dental procedure requiring prophylactic antibiotics) scheduled during the trial.
- 17. Active drug, chemical, or alcohol dependency as determined by the Investigator through history or optional toxicology screen.

- Enrollment in any other investigational drug, device, or observational trial within 30 days or 5 half-lives of the last dose, prior to Randomization (Day 1) or at any time during this trial.
- 19. Pregnant, breast-feeding, or planning to become pregnant during the trial.
- 20. Clinically significant abnormal laboratory values including, but not limited to, white blood cell count  $\geq 15 \times 10^{9}$ /L, absolute neutrophil count of  $< 1 \times 10^{9}$  neutrophils/L, or laboratory evidence of acute kidney injury at Investigators discretion, at Screening.
- Screening nasal PCR test is positive for severe acute respiratory syndrome coronavirus 2 (SARS-CoV-2).
- 22. Any acute, chronic, or unstable medical comorbidity, psychiatric, social, or other circumstances that, in the opinion of the Investigator, may interfere with trial compliance, completion, or accurate assessment of trial outcomes/safety. Examples include but not limited to acute myocardial infarction, acute stroke, uncompensated congestive heart failure, or decompensated liver disease.

*NOTE*: Trial participants may be screened while an inpatient in an acute care facility/hospital but must be discharged from inpatient medical admission prior to Randomization.

- 23. Life expectancy < 24 weeks.
- 24. Known hypersensitivity to CP101 or any component of its formulation or history of severe adverse reactions or other common drug class effects during prior exposure to similar compounds per the judgment of the Investigator.

To be eligible for Randomization, the above listed Inclusion/Exclusion Criteria as well as the following additional Inclusion Criteria Part A - Randomization (Day 1) must be satisfied:

[figure not shown]
